1.0 Background

Brief Summary:

The purpose of this study is to elucidate if a novel biomaterial containing gelatin, manuka honey, and hydroxyapatite enhances secondary intention healing when compared to conventional secondary intention healing for surgical defects after Mohs micrographic surgery on the head and distal lower extremities (below the knee).

Detailed Description:

Secondary intention healing (SIH) is often underutilized and has several advantages compared to primary surgical repair.^{1,2} Wound care is minimal, bleeding and infection are rare, and risks associated with primary closure (e.g. hematoma, suture granuloma, graft or flap failure) are non-existent.³ Importantly, SIH facilitates surveillance of tumor recurrence, whereas flaps and grafts may bury residual tumor.^{1,3} When used in appropriate anatomical locations, SIH leads to high patient satisfaction.^{1,2,4} However, SIH requires regular wound care that can be cumbersome to patients.^{3,5}

Prior studies utilizing biologic dressings have shown patients report better quality of life during the post-operative period related to less pain, decreased dressing changes, and faster healing times.^{5,6} Biologic dressings provide an alternative to surgical autografts and eliminate the risks associated with graft harvesting (e.g. pain, infection, and scarring).^{5,7} For many patients, the cosmetic outcome following healing is important. However, cosmetic outcome with SIH is variable and depends on many factors, namely location (e.g. concavities favorable), skin laxity, and underlying musculature.^{1,2,8} Exuberant granulation tissue, hypopigmented and telangiectatic scars are the most frequent adverse cosmetic outcomes with SIH.^{3,9}

The novel biomaterial APIS[®] (SweetBio, Inc. Memphis, TN) is an advanced synthesis of gelatin, manuka honey, and hydroxyapatite bioengineered to protect wounds, manage exudate, and maintain a moist environment. It is FDA cleared (FDA number K1827250) for wound management across 9 indications including surgical wounds. It has been used successfully in a small case series of 8 patients for post-operative Mohs surgical wounds on the head and distal lower extremities. Time to complete re-epithelialization was 6 weeks (42 days), suggesting a reduction in healing time compared to standard SIH times for the leg and head of 127 and 57 days, respectively.^{10,11} Use of this novel biomaterial to enhance SIH is hypothesized to reduce healing times when compared to standard SIH wound care. This provides a useful option to aid SIH in sites like the lower legs, where healing can be prolonged due to intrinsic factors (e.g., cardiovascular disease, peripheral vascular disease, diabetes) or extrinsic factors (e.g., increased risk of surgical site infection following dermatologic surgery at sites below the knee).^{10,12}

2.0 Rationale and Specific Aims

Randomized, comparative studies evaluating augmented SIH compared to conventional SIH in dermatologic surgery are limited. This study aims to evaluate whether use of a novel biomaterial enhances SIH, particularly in shortening time to complete re-epithelialization. Patients undergoing Mohs micrographic surgery amenable to SIH on the head and distal lower extremities will be randomized into one of four groups (standard SIH or biomaterial APIS[®] enhanced SIH on the head or distal lower extremities). Patients will have regularly scheduled follow-up with questionnaires at each visit. We aim to evaluate whether use of this novel biomaterial decreases complete reepithelialization times, reduces infection rates, and improves cosmetic outcomes.

Outcome Measures

Primary:

1. Time to complete re-epithelialization

Patients will be seen in office 14 days post-operative, then every 14 days thereafter until complete re-epithelialization is achieved. Patients will also submit photos via Vanderbilt HIPAA compliant Box at regular follow-up intervals (post-operative day 7 then every 14 days thereafter until complete re-epithelialization is achieved). Time elapsed from surgery date to complete re-epithelialization will be noted in days.

Secondary:

1. Patient and Observer Scar Assessment Scale (POSAS) Patient Scale Score Version 2.0

Patients will complete the POSAS Patient Scale after complete re-epithelialization is achieved. The POSAS Patient Scale is a validated and widely accepted scar assessment tool. The patient scale has six questions assessing scar pain, itch, color, stiffness, thickness, and irregularity rated from 1 (no, not at all/normal skin) to 10 (yes, very much/worst imaginable). Scale from 6-60 with a final seventh question rating patient's overall opinion of scar quality (1-10).

2. Visual Analog Scale (VAS) – Provider Scar Ranking

Digital standardized photographs of scars after complete re-epithelialization is achieved will be assessed by two blinded dermatologists using the VAS. This scale ranges from 0 or normal skin to 10 or worst possible scar taking into account the scar's pigmentation, vascularity, contour, observer comfort, and overall severity. VAS scores of novel biomaterial will be compared to standard SIH.

3. Size of wound

Post-operative wounds will be measured at regularly scheduled follow-ups. The area and volume for each patient's wound will be calculated.

4. Pain score

Patients will self-report their surgical site/wound pain during in office follow-up visits via a questionnaire. Pain scale will range from 1 (no pain) to 10 (worst pain imaginable).

5. Infection

Post-operative wounds will be assessed for infection at regularly scheduled follow-ups. Any suspected infection (e.g. erythema, purulence, malodor) will be cultured and reported. Antibiotic usage for either prophylaxis peri-operatively or treatment will be recorded.

6. Bleeding

Patients will report any bleeding (yes/no) via questionnaires at regularly scheduled follow-ups. Additionally, if there was post-operative bleeding, was an intervention performed to achieve hemostasis (yes/no) and if yes, what intervention.

7. Ease of Wound Care

Patients will self-report the ease of wound care on a scale of 1 (very easy) to 10 (impossible) via questionnaires at regularly scheduled follow-ups.

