4.0 Inclusion/Exclusion Criteria

Inclusion Criteria:

- 18 years of age or older
- Post-operative wounds following Mohs surgery on the head or distal lower extremities
- Single Mohs post-operative defect
- Post-operative wounds greater than 1cm in width
- Depth of defect at least to subcutaneous tissue
- Patients have the ability to provide their own wound care
- Agreeable to regularly scheduled follow-up visits and transmission of photos via HIPAA compliant Vanderbilt University Medical Center Box
- Patients are able to provide informed consent

Exclusion Criteria:

- Under 18 years of age
- Unable to provide informed consent
- Unable to understand oral and written English
- Post-operative wounds not appropriate for secondary intention healing
- Sensitivity or allergy to APIS[®] biomaterial including collagen and its derivatives, porcine-derived materials or honey
- Immunosuppressed and organ transplant patients
- Post-operative wounds superficial to subcutaneous tissue

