6.0 Study Procedures

Arms and Interventions Two experimental groups

- 1) APIS[®] biomaterial on the head
- 2) APIS[®] biomaterial on the distal lower extremities

Two control groups

- 1) No intervention, standard SIH wound care on the head
- 2) No intervention, standard SIH wound care on the distal lower extremities

Experimental (40 patients): APIS[®] biomaterial. APIS[®] biomaterial placed on post-operative wound.

- 1) Head (20 patients)
- 2) Distal lower extremities (20 patients)
 - a. Device: APIS[®] biomaterial. This biomaterial was FDA cleared in 2019 for management of full and partial thickness wounds, pressure ulcers, venous stasis ulcers, diabetic ulcers, surface wounds, traumatic wounds, surgical wounds, abrasions, and donor site wounds.
 - b. One layer of APIS[®] will be applied to the post-operative wound covered by petrolatum impregnated gauze, a non-stick Telfa pad, gauze, and Opsite tape.

c. The biomaterial will be reapplied if it is completely absorbed at follow up and the wound depth below the epithelial level.

No intervention (40 patients): No APIS[®] biomaterial on post-operative wound.

- 3) Head (20 patients)
- 4) Distal lower extremities (20 patients)
 - a. Post-operative wound will heal via conventional secondary intention. Application of petrolatum impregnated gauze, a non-stick Telfa pad, gauze, and Opsite tape.

This study may be deemed complete prior to reaching above enrollment numbers if statistical significance is achieved or at the discretion of the research team.

Mohs Surgery – Day 0

Patients eligible for study will be offered opportunity to enroll. After informed consent has been obtained, the patient's clinical history, medical history, social history, medication history, and vital signs will be reviewed and documented. Pre and postoperative photos will be obtained and stored in the Electronic Medical Record and Vanderbilt HIPAA compliant Box.

Patients on day of surgery will be provided with a post-operative wound care instruction sheet (for both control and experimental groups). They will also receive a detailed instruction sheet for uploading post-operative photos to Vanderbilt's HIPAA compliant Box.

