Subsequent Post-operative Visits – Post operative Day 14 then every 14 days thereafter until complete re-epithelialization is achieved. Patients enrolled in study will be provided a brief questionnaire to complete at in-person office follow-up visits. Post-operative wounds will be assessed for any complications. Size of wounds in addition to photographs will be obtained until complete re-epithelialization is achieved. Patients will also upload post-operative photos to Vanderbilt's HIPAA compliant Box post-operative day 7 then every 14 days thereafter until complete re-epithelialization is complete.

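### No Day 0 wound dimensions are scheduled for recording, so the wound-size outcome has no specified pre-treatment reference and a baseline-size covariate is not guaranteed

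*Combined protocol and SAP*

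**What the plan says.** All references are to the combined protocol and SAP.

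- **Section 2.0, Outcome Measures, Secondary 3 (Size of wound).** "Post-operative wounds will be measured at regularly scheduled follow-ups", and "The area and volume for each patient's wound will be calculated". No change from baseline, percentage reduction or other form of analysis is defined.
- **Section 2.0, primary outcome.** "Patients will be seen in office 14 days post-operative, then every 14 days thereafter until complete re-epithelialization is achieved".
- **Section 6.0, Day 0.** After consent, "the patient's clinical history, medical history, social history, medication history, and vital signs will be reviewed and documented". Also, "Pre and postoperative photos will be obtained and stored in the Electronic Medical Record and Vanderbilt HIPAA compliant Box". The only other items are the wound-care and photo-upload instruction sheets. No length, width, depth, area or volume is listed.
- **Section 6.0, Subsequent Post-operative Visits (Day 14 onward).** "Size of wounds in addition to photographs will be obtained until complete re-epithelialization is achieved".
- **Section 4.0.** "Post-operative wounds greater than 1cm in width" is an inclusion criterion, and the defect must reach at least the subcutaneous tissue. There is no upper size limit.
- **Section 5.0.** Block randomisation, 1:1, with no balancing on wound size described.
- **Section 10.0.** Healing time is compared with an unadjusted Student's t-test. No analysis of the wound-size outcome is given.

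**The concern.** Wound size is a named secondary outcome, yet every scheduled measurement falls after the randomised treatment has begun. A smaller wound at Day 14 may reflect faster closure or a smaller original defect. With no Day 0 value on file, the analyst could not report closure relative to the starting wound, could not show whether the arms started alike, and could not adjust for starting size.

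Starting size is also a natural prognostic covariate for healing time, in a trial with 20 patients per arm per site and no ceiling on defect size. Using the Day 14 size in its place would be a mistake: treatment may already have altered it, so adjusting for it would remove part of the effect that the trial sets out to estimate. A Day 0 measurement that was never taken cannot be taken later.

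**Working it through.** **1. Is a Day 0 size scheduled anywhere?**

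| Place | Timing | Size information required |
|---|---|---|
| 2.0, Secondary 3 | follow-ups | area and volume |
| 6.0, Subsequent visits | Day 14, then every 14 days | wound size |
| 6.0, Day 0 | day of surgery | none; photographs only |
| 4.0, eligibility | assessment of the final defect | width above or below 1 cm; depth category |

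Eligibility implies that someone looks at width and depth on Day 0. The first is a threshold and the second a category; neither has to be written down as a value, and neither yields area or volume. The photographs give no depth, so Day 0 volume cannot be recovered from them. No scale marker is described, so recovery of area is uncertain.

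**2. How far into healing is Day 14?** Using the healing times quoted in sections 1.0 and 3.0:

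- biomaterial, 42 days: 14/42 = 33%
- standard care, head, 57 days: 14/57 = 25%
- standard care, leg, 127 days: 14/127 = 11%

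That the biomaterial is applied on Day 0 is inferred from section 6.0, not stated outright. On that reading Day 14 is clearly post-treatment.

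**3. Size of chance imbalance.** With n per arm, the difference in mean starting size has standard deviation √(2/n), in SD units of starting size. Probabilities use the normal approximation, two-sided.

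| Comparison | √(2/n) | P(imbalance over 0.25 SD) | P(imbalance over 0.5 SD) |
|---|---|---|---|
| 40 v 40 (overall) | √(2/40) = 0.22 | 26% | 2.5% |
| 20 v 20 (one site) | √(2/20) = 0.32 | 43% | 11% |

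**4. What adjustment could be worth (illustration only).** There is no figure in the plan to reproduce: section 6.0 gives 40 per arm without alpha, power, SD or effect size. Assumptions made here, none of them in the documents:

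- two-sided alpha 0.05;
- 60% power before adjustment for size, which at 40 per arm corresponds to a difference of 0.50 SD;
- a correlation r of 0.3 to 0.6 between starting size and healing time, *within site*.

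The residual variance is multiplied by 1 − r², the equivalent sample size by 1/(1 − r²), and the standardised difference by 1/√(1 − r²).

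| r | 1 − r² | 1/(1 − r²) | Power, starting from 60% |
|---|---|---|---|
| 0.3 | 0.91 | 1.10 | 64% |
| 0.5 | 0.75 | 1.33 | 72% |
| 0.6 | 0.64 | 1.56 | 79% |

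The correlation must be within site because the proposed model also includes site. Head and leg differ widely under standard care (57 v 127 days), and site would already account for that part of the variance.

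**The case against.** The strongest case against is that nothing planned is broken. The primary endpoint runs from surgery to re-epithelialization and needs no baseline size. Section 10.0 plans no covariates, and no section defines the wound-size outcome as a change from baseline. Allocation is randomised, so starting size is balanced in expectation, and the unadjusted standard error already allows for chance imbalance. All of this stands, and it limits the point to precision and to describing or correcting imbalance.

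A reader might infer two stronger things that the documents do not support.

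- *That there is no baseline size information at all, so adjustment is impossible.* The documents are silent on recording, which is not the same as absence. The defect is assessed for eligibility and photographed, and area might be recovered if the photographs carry a scale. Only volume is clearly out of reach.
- *That size differences at Day 14 or later cannot be interpreted, or that the healing-time comparison is biased.* Randomisation rules that out as a general claim.

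It is also fair to object that the power gains rest on an assumed correlation and an assumed starting power. They do, and they cannot carry the weight of the point. The scheduling gap stands whatever the correlation is. The eligibility criteria do not close it, since a threshold check leaves no value to analyse.

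**Conclusion.** The point holds as a gap in the measurement schedule and a cheap gain forgone. It is not a threat to validity. Sections 2.0 and 6.0 agree that wound size is first recorded at Day 14, and no section asks for a recorded Day 0 dimension. The wound-size outcome therefore lacks a specified pre-treatment reference, and a size covariate for healing time is left to chance or to photographs of unstated scale.

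The imbalance that could go undescribed and uncorrected follows from the planned numbers alone: 0.22 SD units overall and 0.32 within a site. The possible gain from adjustment, 9% to 36% of residual variance, depends entirely on the assumed within-site correlation of 0.3 to 0.6. The change is worth making before enrolment or, if enrolment has begun, at once for the remaining patients.

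**What to change.** 1. **Section 6.0, Day 0.** Add a recorded length, width and depth of the final defect, taken before allocation is revealed and before any dressing or biomaterial is applied. Compute area and volume by the same method as at follow-up.
2. **Section 2.0, Secondary 3.** State that wound size is measured on Day 0 as well as at follow-ups, and that the Day 0 value is the reference.
3. **Section 10.0, primary outcome.** Replace the unadjusted t-test with a pre-specified linear model for healing time with treatment, site and log baseline area (or volume). Choose area or volume in advance.
4. **Section 10.0, wound size.** Analyse follow-up size adjusted for the Day 0 value. State that the Day 14 size will not be used as a baseline covariate.

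Cost: a ruler and depth measurement at surgery and one form field per patient, with no extra staff or visit.

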3.0 Animal Studies and Previous Human Studies

APIS[®] was FDA cleared in 2019 (FDA number K1827250) for management of full and partial thickness wounds, pressure ulcers, venous stasis ulcers, diabetic ulcers, surface wounds, traumatic wounds, surgical wounds, abrasions, and donor site wounds.

A small case series of 8 patients used APIS[®] in SIH of Mohs surgical wounds on the head and distal lower extremities. Time to complete re-epithelialization was 6 weeks (42 days), suggesting a reduction in healing time compared to standard SIH times for the leg and head of 127 and 57 days, respectively.^{10,11}

4.0 Inclusion/Exclusion Criteria

Inclusion Criteria:

- 18 years of age or older
- Post-operative wounds following Mohs surgery on the head or distal lower extremities
- Single Mohs post-operative defect
- Post-operative wounds greater than 1cm in width
- Depth of defect at least to subcutaneous tissue
- Patients have the ability to provide their own wound care
- Agreeable to regularly scheduled follow-up visits and transmission of photos via HIPAA compliant Vanderbilt University Medical Center Box
- Patients are able to provide informed consent

Exclusion Criteria:

- Under 18 years of age
- Unable to provide informed consent
- Unable to understand oral and written English
- Post-operative wounds not appropriate for secondary intention healing
- Sensitivity or allergy to APIS[®] biomaterial including collagen and its derivatives, porcine-derived materials or honey
- Immunosuppressed and organ transplant patients
- Post-operative wounds superficial to subcutaneous tissue

5.0 Enrollment/Randomization

Patient enrollment will occur at Vanderbilt University Medical Center One Hundred Oaks Department of Dermatology Mohs Surgical Unit. All patients eligible for study may be considered. Patients with Mohs surgical defects on the head and distal lower extremities amenable and conducive for SIH will be randomized to intervention or control by block randomization. Subjects will be randomized in a 1:1 ratio.

Address of enrollment: Vanderbilt Dermatology One Hundred Oaks [name] [contact]

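### No stratification by anatomical site is stated, so the 1:1 block randomisation as written does not assure the planned four groups of 20

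*Combined protocol and SAP*

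**What the plan says.** Section 5.0 (Enrollment/Randomization) holds the only operative allocation rule, which is block randomisation: "Patients with Mohs surgical defects on the head and distal lower extremities amenable and conducive for SIH will be randomized to intervention or control by" that method. It adds "Subjects will be randomized in a 1:1 ratio" and, on who may enter, "All patients eligible for study may be considered". It gives no stratification factor, block size, number of lists, or enrolment limit by anatomical site (called site below).

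Section 6.0 (Study Procedures) sets the group sizes: "Experimental (40 patients): APIS[®] biomaterial" and "No intervention (40 patients): No APIS[®] biomaterial on post-operative wound". Each arm is divided into "Head (20 patients") and a further 20 with wounds on the distal lower extremities.

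Section 2.0 (Rationale and Specific Aims) says that patients "will be randomized into one of four groups (standard SIH or biomaterial APIS[®] enhanced SIH on the head or distal lower extremities").

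Sections 1.0 and 3.0 cite standard healing times of 127 days for the leg and 57 days for the head. Section 10.0 compares mean days to re-epithelialisation between control and experimental patients by Student's t-test and mentions no site term.

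**The concern.** The three sections do not describe one procedure. Site is fixed by where the tumour was, so a patient can be randomised to an arm but not to one of four arm-by-site groups. Section 6.0 needs 20 patients in each of those groups, but section 5.0 gives no means of reaching them. Someone who built the allocation list from section 5.0 alone would balance the arm totals and leave the head and leg mix within each arm to chance.

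Site is the only prognostic factor for which the protocol gives healing times, and the gap is large: 127 - 57 = 70 days. Section 1.0 also cites a higher infection risk below the knee, and infection is a secondary outcome. If one arm happened to receive more leg wounds, the crude comparison of healing times would move for that reason alone, and the planned t-test would not adjust for it. The within-site groups would also be unequal.

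**Working it through.** **1. The plan's own figures.** 20 + 20 = 40 per arm, and 4 x 20 = 80 in total. These agree. The documents give no significance level, power, effect size or SD, so there is no sample-size calculation to reproduce.

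**2. Chance of the planned groups with one list.** Assume one unstratified list, exactly 40 head and 40 leg patients, and 40 per arm. The number of head patients in the APIS arm is then hypergeometric (80 patients, 40 head, 40 drawn).

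- P(exactly 20) = C(40,20)² / C(80,40) = 0.177. One count of 20 fixes all four groups at 20.
- SD = √(40 x ½ x ½ x 40/79) = 2.25 patients.
- P(17/23 or worse) = 0.263; P(16/24 or worse) = 0.117.

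**3. Conversion to days.** Let k be the number of patients away from a 20/20 split.

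- If the 70-day gap holds in both arms (no treatment effect), the arm difference shifts by 70 x 2k/40 = 3.5k days. The SD is 3.5 x 2.25 = 7.9 days. A 17/23 split gives 10.5 days and a 16/24 split gives 14 days.
- If the gap holds in the control arm only, the shift is 70 x k/40 = 1.75k days, with SD 1.75 x 2.25 = 3.9 days. This assumes that APIS wounds heal in about 42 days at both sites. Sections 1.0 and 3.0 give 42 days for the case series without splitting it by site.

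**4. Does the planned t-test already count this noise?** With a 50:50 mix and a 70-day gap in both arms, site alone contributes an SD of 70/2 = 35 days within each arm. Its share of the standard error is 35 x √(2/40) = 7.8 days, which matches the 7.9 days in step 3. With one list, the t-test therefore already allows for this variation.

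**5. Alternative schemes.** These are simulations of 80 patients with assumed block sizes of 4 and 8, 8,000 runs each. The 70-day gap is applied in both arms.

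| Scheme | All four groups exactly 20 | SD of arm difference from site mix |
|---|---|---|
| One list, exactly 40 per site | about 18% | 7.9 days |
| One list, no cap, half legs (assumed) | about 1.5% | about 7.8 days |
| One list, no cap, 25% legs (assumed) | about 0% | 6.7 to 6.9 days |
| Separate lists, no cap, half legs | about 9% | 1.2 to 1.5 days |
| Separate lists, no cap, 25% legs | about 0% | 1.3 to 1.7 days |
| Separate lists, cap of 40 per site | 100% | 0 |

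Separate lists balance the arms within site. Reaching 20 in every group also needs the cap.

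**6. Why the analysis must follow the design.** Take an assumed within-site SD s, 40 per arm and a 70-day gap in both arms. The unadjusted standard error is √(s² + 35²) x √(2/40); with a site term it is s x √(2/40).

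- s = 20: 9.0 against 4.5 days.
- s = 30: 10.3 against 6.7 days.
- s = 40: 11.9 against 8.9 days.

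Stratified allocation with an unadjusted t-test would keep the larger standard error and so be conservative.

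**The case against.** The strongest reply is that the protocol never says one list is used. Section 5.0 is silent on strata and on the number of lists. Section 2.0's four groups and section 6.0's 20 per group are compatible with a within-site randomisation that was intended but not written down. This stands. A reader might infer that the trial has a single unstratified scheme, and the documents do not support that as fact. They support only that stratification is not stated and that section 5.0, followed as written, does not lead to section 6.0.

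A reader might also infer that site imbalance biases the result. It does not on average: randomisation remains valid, and step 4 shows that the t-test allows for the variation under one list. A false 14-day difference describes one unlucky allocation, with a 12% chance of that split or worse, not an expected error.

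A third inference would be selection bias from skipping or reassigning list entries once a group is full. No section describes such a practice, so this is not a finding.

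The 57 and 127 days come from cited sources that cannot be checked here, and the gap under APIS is not given by site. The day figures are therefore illustrative. The probabilities in step 2 do not depend on the gap, but they do assume one list.

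Finally, a limit of 40 per site is already implied by section 6.0. What is missing is the procedure for closing a site.

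**Conclusion.** The point holds as a gap between the allocation rule and the planned groups. No stratification by site is stated, section 2.0 describes a randomisation that cannot be carried out literally, and section 5.0 followed with one list does not assure the groups of 20 in section 6.0. The chance of reaching them is about 18% with exactly 40 patients per site, and lower without a cap.

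Under the same one-list assumption, site imbalance adds noise with an SD of roughly 4 to 8 days to the unadjusted arm difference. The lower figure applies the 70-day gap in the control arm only, and the upper figure applies it in both arms. This is a loss of precision.

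The point does not depend on knowing what was intended. If within-site randomisation was meant, it needs to be written down; if it was not, the design can be improved at almost no cost. The change should be made, preferably before allocation starts. After that, only the analysis can compensate.

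**What to change.** - **Section 5.0:** replace the allocation sentence with 'Within each anatomical site (head; distal lower extremity), patients will be randomised 1:1 to APIS or standard SIH from a separate permuted-block list. Enrolment to a site closes at 40 patients.'
- **Section 2.0:** replace the four-group wording with 'randomised to APIS or standard SIH, stratified by site'.
- **Section 10.0:** include site as a factor in the primary comparison, so that the standard error reflects the stratification.

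The cost is a few sentences and two allocation lists instead of one, with no extra patients or visits. The downside is that the site that fills first closes to enrolment, which may lengthen recruitment in a single-centre study expected to last 12 months (section 12.0). If the sponsor prefers not to cap, separate lists still keep the arms close to balance within site, but the 20-per-group figures in section 6.0 should then be described as approximate.
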